Patients with previous diagnosis of histoplasmosis will not be considered for this study. We will also exclude pregnant or lactating woman, patients with renal failure (serum creatinine and urea >1.5 times the upper limit of normality), abnormal aminotransferases (up to >3 times the upper limit of normality), and patients with a previous serious reaction to a polyene antifungal drug. Patients who received more than one dose of a polyene antifungal drug in the last 48 hours will be excluded, as well as patients who refuse content to participate in the study. Patients diagnosed with histoplasmosis affecting the central nervous system will not be allowed to participate in the study. In addition, patients who are expected to die within 48 hours of enrolment will also be excluded, based on the judgment made by the attending physician. Patients diagnosed with tuberculosis will be excluded; as well those receiving drugs that cause significant drug-drug interaction (relative or absolute) with itraconazole.

Study settings

Six medical centers in Brazil, will recruit patients for this study: Santa Casa de Misericórdia de Porto Alegre, Hospital de Clínicas de Porto Alegre, Hospital Nossa Senhora da Conceição, Hospital de Doenças Tropicais, Hospital São Jose de Doenças Infecciosas, and Hospital Giselda Trigueiro.

Intervention

AIDS patients with DH will be randomized to one of three study arms: (i) single IV dose of L-AmB at 10 mg/kg; (ii) single IV dose of 10 mg/kg of L-AmB on day 1, followed by 5 mg/kg of L-AmB on day 3; and (iii) L-AmB at 3 mg/kg IV for 2 weeks. Induction therapy will be followed in all patients by oral therapy with itraconazole capsules at 400 mg/daily for a year.

Drug reconstitution and administration

L-AmB (AmBisome; Gilead Sciences, San Dimas, California, USA), a lyophilized liposomal preparation of amphotericin B, will be reconstituted according to the manufacturer's instruction and given intravenously at fixed doses, according to the randomization arm. L-AmB concentration should be of 0.2 mg/ml in 5% dextrose, and the drug should be infused over 2 hours, preferably in a central line. Patients will be monitored for the occurrence of infusion-related toxicity during and after drug infusion.

Primary endpoint

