Clinical and mycological successes will be the primary outcomes for this study. A successful clinical response to induction therapy will be defined according to, as a maximum daily temperature $<37.8^{\circ}\text{C}$ for 72 hours; no increase in severity of clinical signs, symptoms, or laboratory abnormalities attributable to histoplasmosis; and the resolution of at least one of the signs or symptoms of histoplasmosis that qualified the patient for study enrollment [7].

Primary study outcome will be determined at day 14 of the study.

Secondary endpoints

Overall mortality and investigator-attributable mortality due to histoplasmosis will be determined at day 14 of study. Overall Survival (OS) will also be determined at 12, 24, and 48 weeks of study. OS will be considered as the time from randomization until death from any cause.

Secondary endpoint will also include need for an additional antifungal course with L-AmB, during 24 weeks of follow up.

Median percentage of change in renal and hepatic function at 14 days will be compared with baseline values.

Frequency of infusion-related toxicity with L-AmB will be recorded.

Clearance of blood cultures will not be used as a criterion for mycological response in this study, due to the limited sensitivity of blood culture in histoplasmosis [19]. Fungal clearance will also not be used as a criterion for mycological response. Differently from cryptococcosis, in which fungal burden is easily obtained and quantified in cerebrospinal fluid samples,

in histoplasmosis commonly a single positive sample is obtained along patient investigation (e.g., microscopy, culture, and/or histopathology).

Non-culture laboratory markers have proved to be useful adjuncts in monitoring the response to systemic histoplasmosis [20, 21]. In this study, we will evaluate the effect of a decrease of at least 50% in *Histoplasma* urinary antigen concentrations [19] along the first 2 weeks of therapy as a secondary endpoint, and the association of such reductions with clinical response to antifungal therapy.

Rescue therapy

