The study protocol will allow patients to receive additional courses of L-AmB (at 3 mg/kg daily) in case the attendant physician suspect of absence of response with the induction regimen. This will apply for failing patients receiving a single 10 mg/kg of L-AmB; or 10 mg/kg on day 1, followed by 5 mg/kg on day 3. In these cases, L-AmB should be given up to a maximum period of 2 weeks. The estimated frequency of L-AmB as rescue therapy will be based on the frequency of failure with L-AmB at 3 mg/kg in patients with DH and AIDS (i.e., 12%) [7]. Considering that 66 patients will be evaluated in arms (i) and (ii) of the study (high-doses of L-AmB), in a pessimistic scenario we aim to provide 8 additional treatments with L-AmB.

Time for initiating ART

Physicians will be instructed to initiate ART as soon as possible in AIDS patients with DH, since immune reconstitution syndrome is uncommon in patients with DH [22]. In Brazil, initial ART consists of dolutegravir, lamivudine, and tenofovir. History of previous antifungal use and known resistance patterns will also be considered in the decisions about ART.

Statistical analyses

Descriptive statistics will be used to summarize the data. Mean, standard deviation, median, interquartile range and minimum and maximum will be described for continuous variables. Categorical variables will be summarized by absolute and relative frequencies. Kaplan-Meier method will be used in order to describe OS. Despite the non-comparative status of the

trial, exploratory comparisons will be performed across subgroups. Continuous variables will be compared using two sample t-test, paired sample t-test, Mann-Whitney test, Wilcoxon signed-rank test, one-way ANOVA or Kruskal-Wallis test, as appropriate and necessary. Categorical variables will be compared with Fisher exact test or chi-square test, as appropriate. All p-values will be two-sided.

We expect that the three arms will have the same clinical response. For each arm, when the sample size is 29, a two-sided 90% confidence interval will extend 10% from the observed proportion for an expected proportion of response equal to 88% [as extracted from the Johnson trial]. Considering a dropout of 10%, the sample size per arm will be 33. The total sample size for the study will be 99 patients. Data analysis will be performed using SPSS software.

Ethical aspects

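### The day-14 clinical success definition has no rule for patients given rescue L-AmB before day 14, and rescue is provided only in the two short-course arms

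*Combined protocol and SAP*

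**What the plan says.** **Primary endpoint.** The section states "Clinical and mycological successes will be the primary outcomes for this study" and "Primary study outcome will be determined at day 14 of the study". This point concerns the clinical component only. Clinical success has three criteria:

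- The first is introduced by "A successful clinical response to induction therapy will be defined according to, as a maximum daily temperature" and requires readings below 37.8°C for 72 hours.
- The second is "no increase in severity of clinical signs, symptoms, or laboratory abnormalities attributable to histoplasmosis".
- The third is that at least one qualifying sign or symptom has resolved.

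None of the three refers to additional L-AmB.

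**Rescue therapy.** When the attending physician suspects non-response, a patient may "receive additional courses of L-AmB (at 3 mg/kg daily) in case the attendant physician suspect of absence of response with the induction regimen". On eligibility the section says "This will apply for failing patients receiving a single 10 mg/kg of L-AmB" and adds the two-dose arm; arm (iii) is not named. On duration: "In these cases, L-AmB should be given up to a maximum period of 2 weeks". No earliest start is given. The rescue dose level is that of arm (iii), which the Intervention section gives as "L-AmB at 3 mg/kg IV for 2 weeks". The forecast applies a 12% failure rate to 66 patients, giving 8 courses.

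**Elsewhere.** Need for a further L-AmB course is a separate secondary endpoint over 24 weeks. Table 1 places response determination at day 14, need for an additional course at day 14 and week 12, and concomitant medications at baseline and days 3, 7 and 14. The Statistical analyses section has no rule for rescued patients.

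**The concern.** Suppose a short-course patient has not improved by the day-7 evaluation and starts rescue then. Seven days remain, of which three must be afebrile. If the patient meets the three criteria on day 14, the literal definition records a success for the short course, although the response followed added drug. The no-worsening criterion may exclude patients rescued because they deteriorated, but not those rescued because they failed to improve. Arm (iii) has no such route.

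The trial is labelled non-comparative, but its Objectives include comparing the regimens, and the Research Justification looks ahead to a phase III trial. Each short-course estimate is affected whether or not arms are compared. The trial is also open label and rescue rests on physician judgement. Without a rule, the scoring would be chosen after the data are seen.

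**Working it through.** **Inputs from the documents.** Expected response p = 0.88, evaluable n = 29 per arm, two-sided 90% interval extending 10 points, 10% dropout, 33 per arm (all Statistical analyses); 12% failure rate and 8 rescues in 66 (Rescue therapy).

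**Inputs not in the documents.** f, the fraction of failures rescued in time to affect day 14, and s, the fraction of those who then meet the criteria. Each can lie anywhere from 0 to 1.

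**1. The plan's own figures reproduce.**
- n = 1.6449² × 0.88 × 0.12 / 0.10² = 28.57, rounded up to 29.
- 29 / 0.9 = 32.2, rounded up to 33; 3 × 33 = 99.
- Half-width at n = 29: 1.6449 × √(0.88 × 0.12 / 29) = 0.0993, or 9.9 points (0.0993 × 29 = 2.9 patients).
- Rescues: 0.12 × 66 = 7.92, about 8.

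**2. Upward shift relative to rescue as failure.** Shift = (1 − p) × f × s, with 1 − p = 0.12.

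| f | s | Shift (points) | Patients of 29 |
|---|---|---|---|
| 0 (or s = 0) | any | 0 | 0 |
| 0.25 | 0.25 | 0.75 | 0.22 |
| 0.5 | 0.5 | 3.0 | 0.87 |
| 1 | 0.88 | 10.6 | 3.06 |
| 1 | 1 | 12.0 | 3.48 |

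One patient is 1/29 = 3.4 points. The shift equals the half-width when f × s = 0.0993 / 0.12 = 0.83.

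**3. Largest gap between the two scorings at the forecast number of rescues.** Pooled over both arms: 8/66 = 12.1 points. With an even split: 4/33 = 12.1 points in each arm. If all 8 fell in one arm: 8/33 = 24.2 points there. These use randomised denominators; on 2 × 29 = 58 evaluable patients the pooled figure is 8/58 = 13.8 points.

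**4. Opposite error if rescue is scored as failure.** If a fraction r of patients who would have responded unaided are rescued as a precaution, the arm loses p × r: 0.88 × 0.05 = 4.4 points, or 0.88 × 0.10 = 8.8 points (r is assumed). This equals the upward shift it removes when r = 0.12 × f × s / 0.88, which is 3.4% at f × s = 0.25 and 6.8% at f × s = 0.5.

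**The case against.** The text leans clearly towards rescue as failure. The endpoint is response to the induction treatment, the rescue trigger is worded as its opposite, rescued patients are described as failing, and the rescue forecast is set equal to the failure rate. Rescue before day 14 is itself an inference: Table 1 first asks about an additional course at day 14. The upper end of the range is strained, because a patient who dies before rescue cannot become a rescued success and one rescued for worsening may fail the second criterion. The trial has no test, margin or decision threshold for the shift to overturn. Finally, response regardless of rescue is a legitimate endpoint if stated, while rescue as non-response brings an open-label judgement into the scoring of two arms.

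Most of this stands and limits the size, but none of it supplies a scoring rule. The physician's suspicion of non-response is not among the three criteria, and nothing bars rescue before day 14. The last argument is a reason to report both scorings, not to leave the choice open.

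Three stronger readings should be resisted:

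- A reader might infer that the plan means to credit rescue to the short courses. Its wording points the other way.
- A reader might expect distortions of 20 or 30 points. Those are ceilings at 80% or 70% response and would need about 13 or 20 rescues in 66 (0.20 × 66 = 13.2; 0.30 × 66 = 19.8), against a forecast of 8 that the plan already calls pessimistic. They depart from its 88% assumption.
- A reader might take 12.1 points as a limit for each arm. It holds only pooled or with an even split.

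**Conclusion.** The point holds as an unstated scoring rule with a one-sided consequence, and it should be fixed. That the rule is missing is certain; how much it matters is not. At the planned 88% response, plausible values lie below one patient of 29 per short-course arm. The 12-point ceiling requires every failure to be rescued in time and to recover. All values between the extremes rest on assumed f and s. Confidence is therefore medium. The concern is with interpretation of the arm (i) and (ii) estimates and any comparison with arm (iii); the sample size of 29, 33 and 99 is unaffected.

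**What to change.** Add to the Primary endpoint section, for all arms alike: *A patient who receives L-AmB beyond the randomised induction regimen before the day-14 assessment is a non-responder in the primary analysis.*

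Record the start date and reason for each rescue course; the concomitant-medications row of Table 1 can hold them. Report response regardless of rescue, by arm, as a sensitivity analysis. The two scorings bracket the unaided response, provided that rescue does not prevent a response.

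The cost is one sentence, two data fields and one extra results line per arm. The downside is that precautionary rescue of true responders counts against arms (i) and (ii), and this could offset the bias removed. Both figures should therefore be shown together. Nothing changes in who may be rescued, when, or with what.

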Conduction of this study is conditioned to ethical approval by local IRBs. Since this trial will not aim to modify any regulatory aspect related to L-AmB in Brazil, ANVISA (Brazilian Health Regulatory Agency) will not be consulted. The study will also be registered at clinicaltrials.gov.

Study activities

Clinical evaluations will take place at baseline, day 3, day 7, and day 14 (End of Study Visit). End of follow up will occur at week 48, and mortality will be determined at weeks 12, 24, and 48.

The study will recommend careful attention to hydration status, and close monitoring of renal function, hepatic function, and electrolytes. Unless clinically advisable, physicians are requested to give one liter of saline 0.9% solution intravenously before L-AmB infusion. Patients should also be on prophylaxis with daily trimethoprim-sulfamethoxazole.

Table 1 shows the procedures predicted for this study. Clinical and laboratory adverse events will be graded using the NIH DAIDS Toxicity Table [23]. Itraconazole therapeutic drug monitoring will be offered to sites at day 7 and day 14 of study. The attending physicians will use this information according to their personal judgment.

Table 1. Study activities.

	Baseline	Day 3	Day 7	Day 14	Week 12	Week 24	Week 48
Informed Consent	X						
History	X						
Physical Exam	X		X	X			
Maximum Temp	X	X	X	X			
Glasgow coma scale	X		X	X			
Chemistry (including magnesium) and blood counts	X		X	X			
HIV documentation	X						
CD4 count determination							
Pregnancy Test	X						
Chest X-ray	X			X			
Study Drug accountability	X						
Concomitant medications	X	X	X	X			
Adverse Events		X	X	X			
Survival determination				X	X	X	X
Molecular test for TB	X						
Urine for Histo antigen test	X		X	X			
Histoplasma PCR (as needed)	X						
Fungal culture (as needed)	X						
Microscopy (as needed)	X						
Histopathology (as needed)	X						
Itraconazole TDM			X	X			
Lysis centrifugation (if available)	X						
Study responde determination				X			
Need for additioal course of L-AmB				X	X		

Study Plan Schedule Strategy

Table 2 shows the predicted timeline for this study.

Table 2. Study plan.

References

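### Adverse event and chemistry collection ends at day 14, but rescue L-AmB in arms (i) and (ii) can run past it, so the safety record of the short-course strategies including rescue is incomplete

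*Combined protocol and SAP*

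**What the plan says.** The Study activities section states: "Clinical evaluations will take place at baseline, day 3, day 7, and day 14 (End of Study Visit"). Beyond that visit it provides for survival: "End of follow up will occur at week 48, and mortality will be determined at weeks 12, 24, and 48".

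In Table 1, the adverse events row is marked at days 3, 7 and 14. The row "Chemistry (including magnesium) and blood counts" is marked at baseline, day 7 and day 14, and concomitant medications are not marked after day 14. The only rows marked later are survival (weeks 12, 24 and 48) and need for an additional L-AmB course (day 14 and week 12).

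The same section sets the grading system: "Clinical and laboratory adverse events will be graded using the NIH DAIDS Toxicity Table". The laboratory safety endpoint, under Secondary endpoints, has the same limit: "Median percentage of change in renal and hepatic function at 14 days will be compared with baseline values".

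Under Rescue therapy: "The study protocol will allow patients to receive additional courses of L-AmB (at 3 mg/kg daily") when the treating physician suspects that induction has not worked. This applies to arms (i) and (ii) only. On duration: "In these cases, L-AmB should be given up to a maximum period of 2 weeks". No earliest or latest start day is given. Secondary endpoints separately counts the need for an additional L-AmB course over 24 weeks.

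**The concern.** Safety of the three regimens is a stated objective, and the Research Justification section offers better safety and tolerability as one reason for trying fewer, higher doses. The Background section associates L-AmB toxicity with repeated dosing. Rescue is repeated dosing given on top of a high initial dose, in patients whose total exposure then exceeds that of the standard arm. If collection of adverse events and laboratory values stops while rescue is still running, or before it starts, the trial cannot describe the non-fatal toxicity of what those patients actually received.

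At stake is the account of a short-course strategy, meaning the short induction plus the rescue that the protocol provides when it fails. A future phase III trial, which the protocol says these results may support, would need that account.

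**Working it through.** **Plan's own figure.** Rescue therapy takes a 12% failure frequency and 66 patients in arms (i) and (ii): 0.12 × 66 = 7.92, rounded to 8, as the protocol states. Per short-course arm, 0.12 × 33 = 3.96, about 4 patients. With 66 patients at 12%, the 95th percentile of the binomial count is 12, so 8 to 12 is a reasonable planning range at that rate.

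**Inputs for the overlap.** The last adverse event and chemistry visit is day 14 (Table 1). Rescue lasts at most 14 days (Rescue therapy). The start day *s* is not given, so it is varied here as an assumption, with day 1 as the first study dose.

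**Formula.** A full course runs from day *s* to day *s* + 13. The days after day 14 number *s* − 1 for *s* up to 14, and 14 for *s* = 15 or later.

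| Assumed start | Last rescue day | Days after day 14 | Share of course | Treatment-days, 8 full courses |
|---|---|---|---|---|
| Day 4 | 17 | 3 of 14 | 21% | 24 |
| Day 7 | 20 | 6 of 14 | 43% | 48 |
| Day 10 | 23 | 9 of 14 | 64% | 72 |
| Day 14 | 27 | 13 of 14 | 93% | 104 |
| Day 15 or later | 28 or later | 14 of 14 | 100% | 112 |

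Half of a full course falls outside the window only when it starts on day 8 (7 of 14) or later. Courses shorter than 14 days leave fewer days uncovered.

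**Cumulative dose after a full rescue course.**
- Rescue alone: 3 × 14 = 42 mg/kg.
- Arm (i) plus rescue: 10 + 42 = 52 mg/kg.
- Arm (ii) plus rescue: 10 + 5 + 42 = 57 mg/kg.
- Arm (iii): 3 × 14 = 42 mg/kg, assuming daily dosing, which the Intervention section does not state.

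If rescue starts on day 14, the dose given by the last safety visit is 10 + 3 = 13 of 52 mg/kg in arm (i) and 15 + 3 = 18 of 57 mg/kg in arm (ii).

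**Follow-up after the last planned induction dose.** Arm (i): 14 − 1 = 13 days. Arm (ii): 14 − 3 = 11 days. Arm (iii), dosed on days 1 to 14: 14 − 14 = 0 days.

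**The case against.** The strongest reply is that the objective concerns the regimens as induction therapy, and that the primary outcome and the renal and hepatic endpoint are all set at day 14. For that question every arm has the same window. The design is called non-comparative, comparisons are exploratory, and no safety decision rule depends on the later data. This stands: the day-14 summary answers the induction question without distortion from this gap.

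Some coverage also exists. Rescue begun before day 14 is partly seen at the day 7 and day 14 visits. Infusion-related toxicity is to be recorded with no stated cut-off, close renal and hepatic monitoring is recommended, and deaths are captured to week 48. None of this schedules the collection of other non-fatal events or laboratory values after day 14.

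A reader might infer three stronger things that the documents do not support:

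- **The plan makes the short courses look safer than arm (iii).** Arm (iii) has almost no follow-up after its last dose, whereas patients in arms (i) and (ii) who are not rescued have 13 or 11 days. Toxicity appearing after dosing is thus most likely to be missed in arm (iii), which works the other way.
- **At least half of all rescue dosing goes unobserved.** That depends on the start day, which is not given. A start on day 4 leaves 21% uncovered and a start on day 7 leaves 43%.
- **Rescue is open for 24 weeks.** The 24 weeks is the period over which additional courses are counted as an endpoint. The rescue provision is tied to suspected failure of induction and has no stated time limit either way.

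Finally, adding rescue-period events to the by-arm totals would give longer observation to patients selected by a post-randomisation event, in two arms only. That objection is sound and shapes the fix.

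**Conclusion.** The gap is real and narrow. As written, the plan provides for drug exposure in arms (i) and (ii) that can fall partly or wholly after the last scheduled safety collection. It affects about 8 of 66 patients at the protocol's 12% (a figure the protocol itself calls pessimistic), or about 4 of 33 per short-course arm. For a full course, the uncovered part ranges from 3 to 14 of 14 days over assumed start days from day 4 to day 15 or later. These patients would have the highest cumulative exposure in the trial, if arm (iii) is dosed daily and rescue runs to its maximum.

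The incomplete item is the safety of the short-course strategies including rescue. No overall direction of bias should be claimed, and the sample size is unaffected. The change is worth making because safety is an objective and the missing information is cheap to record.

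**What to change.** 1. In Study activities and Table 1, state that for any patient given rescue L-AmB, adverse events (DAIDS grade) and the creatinine and aminotransferase values already taken for care are recorded until the rescue course ends, with its start and stop dates and doses.
2. Keep the day-14 safety summary by arm as the main table, with the same window for all arms.
3. Report the rescue-period data as a separate descriptive summary by randomised arm, giving the number of patients and their exposure time. Do not pool these events into the by-arm totals.
4. Reconcile the related places: the additional-course endpoint runs to 24 weeks, but Table 1 marks its collection only at day 14 and week 12.

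**Cost.** Extra case report form pages for roughly 8 to 12 patients who are already receiving intravenous drug; no added visits for other patients and no change to any dose, rescue rule or the primary endpoint. The drawback is that rescued patients are observed for longer than the rest, which the report should state.

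### Table 1 schedules no chemistry, blood counts or physical examination between baseline and day 7, although the text recommends close laboratory monitoring and arm (ii) is dosed again on day 3

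*Combined protocol and SAP*

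**What the plan says.** The Study activities section of the combined protocol and SAP makes two relevant statements. On visits: "Clinical evaluations will take place at baseline, day 3, day 7, and day 14 (End of Study Visit"). On monitoring: "The study will recommend careful attention to hydration status, and close monitoring of renal function, hepatic function, and electrolytes". The second is a recommendation and names no days. The same section says that clinical and laboratory "adverse events" are graded with the DAIDS table, again without naming days.

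Table 1, in that section, marks the rows "Chemistry (including magnesium) and blood counts" and "Physical Exam" at baseline, day 7 and day 14. The day-3 column is marked for maximum temperature, "Concomitant medications" and adverse events only.

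The Intervention section defines arm (ii) as a "single IV dose of 10 mg/kg of L-AmB on day 1, followed by 5 mg/kg of L-AmB on day 3" and arm (iii) as "L-AmB at 3 mg/kg IV for 2 weeks". Arm (i) is one 10 mg/kg dose.

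The Objectives section names safety of the three regimens as an aim. The defined renal and hepatic endpoint, under Secondary endpoints, is the median percentage change from baseline at 14 days.

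**The concern.** The text and the schedule do not fit together well. A reader of the text would expect renal, hepatic and electrolyte values to be followed closely through induction and would count day 3 as a clinical evaluation. A site working from Table 1 would take no study blood sample and do no study examination until day 7.

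What is at stake is the early safety record. Baseline laboratory values matter enough to the protocol that raised creatinine and urea, or abnormal aminotransferases, exclude a patient. The same values are not scheduled again until arms (i) and (ii) have finished induction. The protocol also describes the single-high-dose strategy as untried in histoplasmosis and offers its results as a basis for a phase III trial, so its account of early laboratory toxicity will be relied on later.

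**Working it through.** The plan gives no figure to reproduce here. The check sets Table 1 against the dosing days.

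**Step 1: read the relevant rows of Table 1 up to day 14.**

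| Row | Baseline | Day 3 | Day 7 | Day 14 |
|---|---|---|---|---|
| Physical examination | X | – | X | X |
| Chemistry and blood counts | X | – | X | X |
| Maximum temperature | X | X | X | X |
| Concomitant medications | X | X | X | X |
| Adverse events | – | X | X | X |

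Day 3 has three marked items, none of them a laboratory test or an examination. The blanks do not look like an extraction fault, because rows with and without a day-3 mark sit close together and keep their column positions. No other section schedules a laboratory test between baseline and day 7.

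**Step 2: dose given before the first scheduled post-baseline chemistry (day 7).** Doses and days are from the Intervention section.

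- Arm (i): 10 of 10 mg/kg. With a single dose this is unavoidable.
- Arm (ii): 10 + 5 = 15 mg/kg, and 15/15 = 100% of induction. The day-3 dose is 5/15 = 33% of the total, in up to 33 patients.
- Arm (iii): the Intervention section does not state the frequency. If dosing is daily, days 1 to 6 give 6 × 3 = 18 mg/kg out of 14 × 3 = 42 mg/kg, or 43%. If the day-7 infusion comes before the day-7 sample, the figure is 7 × 3 = 21 mg/kg, or 50%.

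**Step 3: length of the gap.** If the first infusion is on day 1, the first scheduled value comes 7 − 1 = 6 days later. The Intervention section states day 1 only for arm (ii), so for the other arms this is an assumption.

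**Step 4: what the gap can and cannot affect.**

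- The day-14 renal and hepatic endpoint uses baseline and day-14 values, both scheduled. A day-3 value would not change it.
- An abnormality still present at day 7 would be found by the scheduled sample, though its onset would not be dated.
- An abnormality that arises and resolves before day 7 appears in no scheduled value. It becomes a graded laboratory adverse event only if a site happened to test and the result was recorded. The documents do not say how unscheduled results are captured.

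**The case against.** The strongest reply is that there is no strict contradiction. The protocol recommends close monitoring and does not mandate it. Table 1 lists study procedures, and a recommendation to physicians can stand beside it. The day-3 evaluation is not empty, and nothing says that a clinical evaluation must include chemistry or an examination. All arms share one schedule, the defined renal and hepatic endpoint is untouched, and the Background cites high single doses given without significant toxicity.

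Most of this stands, and it rules out several stronger readings that a reader might infer:

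- *That arm (ii) patients will be dosed again with no laboratory information.* The documents show only that none is scheduled; sites may well test under the general recommendation.
- *That grading laboratory events at day 3 is required and impossible.* No section requires laboratory grading on that day. The day-3 adverse-event entry can be met by clinical events and by any results available.
- *That the schedule makes arms (i) and (ii) look safer than they are.* This needs an assumption about when toxicity appears, which the documents do not state. A transient rise before day 7 would be missed in arm (iii) too.
- *That the dose itself is untried.* The protocol says this of the single-high-dose strategy in histoplasmosis.

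The reply does not remove the gap. If sites test anyway, they do so on days of their own choosing, in six centres, in an open-label trial, and without a stated route for the results into the trial data. The Background also links toxicity to repeated administration, so the cited reassurance about single doses does not settle the matter for arms (ii) and (iii).

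**Conclusion.** The point holds as a gap between the monitoring text, the dosing days and Table 1. No chemistry, blood count or physical examination is scheduled between baseline and day 7. By then arm (ii) has received all 15 mg/kg of its induction and arm (iii), if dosed daily, 18 to 21 of 42 mg/kg.

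The consequence is limited. Early laboratory adverse events that resolve before day 7 may be under-recorded, or recorded unevenly across arms and sites, and the direction of any resulting bias in the exploratory comparisons is unknown. How many events this involves cannot be estimated from the documents. The conclusion rests on Table 1 as extracted and, for arm (iii) and the 6-day interval, on daily dosing from day 1. It should be corrected because safety is a stated objective and the correction is small.

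**What to change.** Reconcile the monitoring text, the day-3 evaluation, the day-3 dosing in arm (ii) and Table 1.

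- Mark the existing chemistry and blood count row at the existing day-3 visit, in all three arms, so that early values are collected uniformly.
- State what the day-3 clinical evaluation consists of, including whether it involves a physical examination.
- Have the sponsor state the timing of the day-3 sample relative to the arm (ii) infusion, and any clinical action on the result. Both are for the sponsor to decide, and this review proposes no rule.
- Record in the case report form all chemistry obtained between days 1 and 7, scheduled or not, with dates, and include it in the DAIDS-graded laboratory adverse events.

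The cost is at most 3 × 33 = 99 additional routine blood samples, at a visit that already exists and with a test already in the schedule, plus the data entry. The documents give no laboratory costs or site logistics, so the expense cannot be put more exactly. The day-14 endpoint and the sample size need no change.
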